### Central Core Laboratory

Given the variability of assays between labs, analyses for additional outcome measures will be performed in a research laboratory (see **Table 2**).

**TABLE 2. Laboratory evaluations and sample storage in research.**

Research lab

• SHBG

• Total and Free Testosterone

• DHEAS

• Blood for DNA extraction for later genetic analysis ☒      Extra blood for repository

### DNA Core Facility

We will obtain blood for DNA extraction at **Hospital Visit 1**, since all subjects will undergo standard phenotyping. Blood (in EDTA tubes) will be sent to the Biochemistry Laboratory at Preclinical Sciences, UWI where DNA will be extracted and stored for future analyses. Our primary purpose is to serve as a repository to participate in genome wide association studies. In both cases, there will be no release of personal identifiers, and we will obtain a Certificate of Confidentiality, as we did in prior studies. This will be a part of the initial protocol, though subjects will have the option to opt out of this segment of the study or limit the use of their specimen on the consent form. This resource may also prove useful for genome wide association studies or other studies of the genetics of PCOS, oligomenorrhea, and hyperandrogenism.

At this time no genetic analyses are proposed as the number of subjects being collected are insufficient for any significant genetic study. However, as it is our hope that this study will serve as the anchor for subsequent investigations of women’s health and PCOS in Trinidad, we intend to isolate and store DNA in the subjects examined in the study. The samples will be stored at The University of the West Indies. If in the future a decision is made to study the DNA samples accumulated, perhaps along with other samples collected, then we will apply for an amendment for genetic analysis.

### Study Specific Biospecimens

The study staff will store the specimens with following specifications:

- According to the temperature requirements
- Maintain a written and electronic log of sample receipt

- Maintain an electronic log of sample location
- Maintain a written and electronic log of equipment temperatures (temperatures or conditions will be measured daily at the same time)
- Ensure that the freezers or refrigerators have adequate temperature controls
- Ensure quality assurance of equipment, which includes records of regular maintenance and quality evaluations
- Place the sample in a clearly identified location in the freezer or refrigerator (i.e., bar coded container) ☒ Log the sample/s into a database with location of sample for easy retrieval.

### ***Adverse Events (AE)***

An adverse event (AE) is defined as any unfavorable and unintended sign (including an abnormal laboratory finding), symptom, or disease temporally occurring during the course of the study, whether associated or not with the procedures performed during the study. AEs may include the following types of occurrences:

- Suspected adverse drug reactions.
- Other medical experiences, regardless of their relationship with the study procedures performed, such as injury, surgery, accidents, extensions of symptoms or apparently unrelated illnesses, and significant abnormalities in clinical laboratory values, psychological testing or physical examination findings.
- Reactions due to medication (e.g. solutions administrated for the OGTT and ACTH stimulation test) overdose, abuse, misuse, withdrawal, sensitivity or toxicity.

Investigators must systematically assess the severity of AEs according to the following definitions:

- ***Mild:*** The subject is aware of the event or symptom, but the event or symptom is easily tolerated.
- ***Moderate:*** The subject experiences sufficient discomfort to interfere with or reduce his or her usual level of activity.
- ***Severe:*** Significant impairment of functioning: the subject is unable to carry out usual activities and/or the subject's life is at risk from the event

### ***Serious Adverse Events***

A serious adverse event (SAE) is one that meets one or more of the following criteria:

- Results in death
- Is life-threatening (places the subject at immediate risk of death from the event as it occurred)
- Results in inpatient hospitalization or prolongation of existing hospitalization
- Results in a persistent or significant disability or incapacity

- Results in a congenital anomaly or birth defect

An important medical event that may not result in death, be life threatening, or require hospitalization may be considered an SAE when, based upon appropriate medical judgment, the event may jeopardize the subject and may require medical or surgical intervention to prevent one of the outcomes listed in this definition. In such a case the participant would be referred to the Eric Williams Medical hospital.

#### **Example AE & SAEs in proposed study:**

Overall, the likelihood of AEs and SAEs in this study is very small. Examples of possible AEs may include:

- Bruising at the site of blood drawing (mild AE)
- Flushing with the administration of ACTH-1-24 for acute ACTH stimulation test to exclude NCAH (mild AE).
- Discomfort with transvaginal ultrasound (mild AE).
- Emotional distress upon knowing of the diagnosis of PCOS (mild to moderate AE).

Since the protocol does not entail any intervention, it is very unlikely that any SAE will occur.

#### **Reporting Procedures**

The current study provides minimum to modest additional patient risk than standard of care. All SAEs throughout study participation from the start of the study will be reported within 24 hours (or 1 business day) of learning of the event to the local IRB. Reporting will be accomplished by completing the Serious Adverse Event Report. Only study number will identify subject and no other identifying information will be included on the form. The investigators will include the following information when reporting an adverse event, or any other incident, experience, or outcome as an unanticipated problem to the IRB.

- Appropriate identifying information for the research protocol, such as the title, investigator's name, and the IRB project number;
- A detailed description of the adverse event, incident, experience, or outcome;
- An explanation of the basis for determining that the adverse event, incident, experience, or outcome represents an unanticipated problem;
- A description of any changes to the protocol or other corrective actions that have been taken or are proposed in response to the unanticipated problem.

To satisfy the requirement for prompt reporting, unanticipated problems will be reported using the following timeline:

- Unanticipated problems that are serious adverse events will be reported to the IRB within 24 hours of the investigator becoming aware of the event.
- Any other unanticipated problem will be reported to the IRB within two weeks of the investigator becoming aware of the problem.
- All unanticipated problems should be reported to appropriate institutional officials (as required by an institution's written reporting procedures), the supporting agency head (or designee), and OHRP within one month of the IRB's receipt of the report of the problem from the investigator.

### **Quality assurance**

1. Instrument validation – A standardized uniform assessment tool (the CFR) was developed for this study. The CFR will be de-identified and pretested.
2. Data collection – the study register will be used to compare participants with non-participants and this will help exclude self-selection bias. The CRF will be used for the collection of data from all the participants. Each study participant will be given a unique identification number to enable follow-up, retrieval of data including missing information and clarification of information. The questionnaire section of the CRF will be completed by a trained researcher to ensure completeness and accuracy of data. The clinical and anthropometric section will be completed by a medically trained researcher. Participants with an initial hirsutism (mFG) score of 3 or more will be re-assessed by a single physician. The pelvic ultrasonography will be performed by experienced Gynecologist trained in pelvic ultrasonography. The antral follicular count (AFC) will be done in the transverse section of the ovary. The blood samples and initial laboratory analysis will be performed by suitably trained research/laboratory assistance. The blood specimens will be collected in the appropriate tubes/containers, and Aprotinin will be added to plain tubes to prevent the breakdown of small proteins that many be useful for measures. The initial blood specimen will be labelled with the participants' unique identification (ID) number, last menstrual period (LMP), date and time of sample collection; while the small aliquots in plastic containers will be labelled with the unique ID number and date. There will also be a laboratory system that records how often the sample has been retrieved, thawed and refrozen. A subject tracking log for longitudinal observational study (Appendix IV) will be used to monitor the data collection process/procedure.
3. Staff training – The members of the research team (PI, Co-investigators and Research Assistants) will undergo a few days training on the various aspects of the study procedure and protocol. The training will cover the following areas: responsible to conduct research, the study protocol, education of

potential study participants, recruitment of study participants, completion of the consent form and CRF, physical examination and anthropometric measurements, biological sample collection and labelling, pelvic ultrasonography, and laboratory techniques and procedures for biological specimen handling, processing and storage. The degree of intra-observer accuracy and consistency, and inter-observer consistency will be established for key physical measures such as hirsutism score, clinical examination and anthropometric measurement, volume of blood sample measurement and pelvic ultrasonography.

4. External quality assessment laboratory - A reference laboratory will be used for the batched analysis of stored sample for external quality assurance. The laboratory of [name] will serve as the reference laboratory.
5. An external advisory group will be established a prior to:
  - a. Advise on the study design
  - b. Help train local staff in study techniques
  - c. Assist in resolving issues that arise during the study
  - d. Assist in identifying collaborative units and laboratories.

[name] and the other collaborators from USA will form the external advisory group.

6. Data management - The CRF will be used to collect data from each study participant. All CRF will be checked for missing data within 24 hours of completion, and any missing data will be detected and collected immediately. The sociodemographic and baseline characteristics, and the clinical findings and anthropometric measurements will be documented in hard copy (CRF) and then imputed into the appropriate software (such as Microsoft Access and SPSS) at regular intervals. The radiological and laboratory data will be documented in the hard copy CRF of each study participant and subsequently imputed to the software. The study register and the CFRs will be kept confidential to avoid identification of the participants beyond the purposes described above. Data entered into the software will only bear the unique ID number. All data and records will be linked with the participants' unique ID number. The electronic database will be password protected. Quality control staff will perform periodic checks for accuracy of data entry (by comparing the hard copy and the electronic chart) and for data accuracy (by re-interviewing the participants). Statistical analysis will be done using SPSS.

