#### Strategies for Sampling, Recruitment and Retention

Participants will be sampled proportionally from all 8 zones as shown above in Trinidad. Approximately 124 women in the reproductive age (18 – 45 years old) will be randomly sampled from each zone. Houses will be numbered and random numbers of these houses will be generated using random number calculator. In each sampled house, females would be prescreened and those that satisfy our inclusion criteria would be selected. Telephone numbers of participants will be obtained and follow-up calls made.

Sample size calculations were based on the following formula (32):

$$n = [(Z_{1-\alpha})^2(P(1 - P)/D^2)]$$

where n = individual sample size,  $Z_{1-\alpha} = 1.96$  (when  $\alpha = 0.05$ ), P = assumed prevalence, and D = absolute error.

Sampling units are defined as individual unselected women between the ages of 18 and 45 years, identified in the community. We target power analysis on women who do not use hormonal contraception. We assume a conservative response rate of 50% of sampled women. This response rate includes the following parameters:

use of hormone/contraceptive use (15%), excluded due to hysterectomy or ovariectomy (3%), excluded due to pregnancy (2%), refusal to participate (20%), and study drop-out/lost to follow-up (10%).

A conservative prevalence estimate for PCOS based on a review of nine studies conducted in the general population using the Rotterdam 2003 definition is 13.4% (4, 5, 33-39). Using the above formula, a sample size of 495 individuals will be required to determine the prevalence with an absolute error of  $\pm 3\%$ . Assuming a 50% enrollment rate, 990 women would need to be approached for study inclusion.

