### Study procedure

Potential study participants from selected geographical locations will be invited to participate in the study. A confidential study register (see attached) containing details of potential study participants (name, age, height, weight, blood pressure and contact phone number) will be kept. Potential study participants will be counselled on the objectives of the study and the study protocol. If the potential participant refuses to participate, no further contact will be made with the participant. Informed consent (see attached) will be obtained from each eligible study participant before recruitment for the study. A subject tracking log for longitudinal observation study will be used to track eligible subjects.

After an informed consent, data will be collected from each study participant using a standard format in a clinical report form (CRF) for uniform data collection from all participants. Each CRF will contain a unique serial identification number. The CRF will be filled by a suitably trained researcher (including the PI, co-investigators and medically trained research assistants). All CRFs will be checked for missing data within 24 hours of completion, and any missing data will be detected and collected immediately.

Each participant will undergo anthropometric measurements (weight, height, waist, circumference and hip circumference) and physical examination for hirsutism, acne, alopecia, acanthosis nigricans, and thyroid enlargement. Participants with an initial hirsutism (mFG) score of 3 or more ( $\geq 3$ ) will be re-assessed by a physician.

After overnight fasting (of 8 hours or more), 10 ml of venous blood sample will be collected from each study participant; within the first seven days of spontaneous or induced menstrual cycle. About half (5 ml) of the venous blood will be collected in an EDTA-containing tube for plasma/DNA and the remaining in a plain tube for serum. Aprotinin will be added to plain tubes to prevent breakdown of small proteins that may be useful for measures. Aprotinin is a small protein bovine pancreatic trypsin inhibitor that inhibits trypsin and related proteolytic enzymes. During the mid-luteal phase of the menstrual cycle (between day 20 and 24), 5 ml of venous blood sample will be collected in a plain tube for serum progesterone.

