***Study specific medical examination will include:***

- Waist and hip circumferences measurement
- Hirsutism assessment
- Acne assessment
- Alopecia assessment
- Acanthosis nigricans assessment

Data Collection:

Types of data:

Independent variables

1. Socio-demographic variables
2. Baseline characteristics

Dependent variables

3. Primary outcome
  - I. Prevalence of PCOS
4. Secondary outcome
  - II. Phenotype of PCOS
  - III. Genotype of PCOS
  - IV. Prevalence of obesity
  - V. Prevalence of hirsutism
  - VI. Prevalence of diabetes

Data collection instrument:

The methods of collecting data for assessment of study objectives include the use of standardized interview-based medical forms; surveys; physical examination.

The CRF developed for this study include; clinical and anthropometric section; radiological report section and laboratory result section. The questionnaire section will seek information on socio-demographic variables, reproductive history with emphasis on menstrual cycle (dating and regularity) and gynecological history, hirsutism, acne, medications, and family history. The anthropometry and clinical section will document the physical findings such as hirsutism, acne, alopecia, acanthosis nigricans, and thyroid enlargement. The pelvic ultrasonographic findings will be recorded in the laboratory result section. Subjects will also complete the

following standardized data instruments or forms as appropriate: FG Score self-assessment, SF-12, Beck depression inventory, Epworth sleepiness scale, and uterine fibroid assessment.

Expected duration of subject participation is approximately from 1 to 3 cycles or 12 weeks. Approximate time to complete enrollment is 9 to 12 months. Approximate time to complete study is 18 to 24 months.

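### The register comparison offered against self-selection can show differences in age, BMI and blood pressure, but not refusal driven by menstrual or androgenic symptoms

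*Combined protocol and SAP*

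**What the plan says.** Item 2 of Quality assurance states that "the study register will be used to compare participants with non-participants and this will help exclude self-selection bias". Study procedure gives the register's content for potential participants as "name, age, height, weight, blood pressure and contact phone number". The form itself is an attachment that is not shown. The same section adds: "If the potential participant refuses to participate, no further contact will be made with the participant".

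Menstrual history, hirsutism, acne and socio-demographic items are placed in the case report form (CRF), described under Data collection instrument. Study procedure has the CRF completed after consent, and Quality assurance says: "The CRF will be used for the collection of data from all the participants".

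Under Strategies for Sampling, Recruitment and Retention, houses are sampled within 8 zones, and in each sampled house "females would be prescreened and those that satisfy our inclusion criteria would be selected". Nothing says that prescreen answers are kept for women who do not take part. The same section breaks the assumed 50% loss into hormone or contraceptive use 15%, hysterectomy or ovariectomy 3%, pregnancy 2%, refusal 20% and drop-out 10%.

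Data management and Statistical analysis describes general group comparisons and regression. It has no comparison of participants with non-participants, no weighting and no sensitivity analysis for non-response.

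**The concern.** A comparison of participants with non-participants informs only about the characteristics it contains. Symptoms are a plausible reason to accept or decline. The work-up is free and its results are returned, which may attract a woman with irregular cycles or unwanted hair. There is no incentive, and participation can involve fasting blood, a pelvic examination and up to three visits, which may deter others. The direction of the net effect is not known.

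The primary outcome is a prevalence, so participation that differs by PCOS status biases it directly. If age, BMI and blood pressure turned out similar, a reader of the plan could take this as evidence against self-selection, although the register would have said almost nothing about the selection that matters most. The missing items cannot be collected later, because contact ends at refusal.

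**Working it through.** **The plan's own figure.** Inputs from Strategies for Sampling, Recruitment and Retention: P = 0.134, D = 0.03, z = 1.96.

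n = 1.96² × 0.134 × 0.866 / 0.03² = 495.3, which agrees with the stated 495. At 50% response, 495 / 0.50 = 990, as stated.

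**Acceptance implied by the loss assumptions.** Of 100 women approached, 15 + 3 + 2 = 20 are lost to contraception, surgery or pregnancy. Of the other 80, 20 refuse, so 60/80 = 75% accept.

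**Effect of differential participation.** Let r be the participation rate of women with PCOS divided by that of women without. The documents do not give r, so the values are assumptions. The expected estimate is p′ = P·r / (P·r + 1 − P).

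- r = 0.8: 0.1072 / 0.9732 = 11.0% (−2.4 points)
- r = 1.25: 0.1675 / 1.0335 = 16.2% (+2.8 points)

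**Ratio that uses up the planned 3 points.** r = [p′/(1 − p′)] / [P/(1 − P)].

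- p′ = 0.164: (0.164/0.836) / (0.134/0.866) = 1.27
- p′ = 0.104: (0.104/0.896) / (0.134/0.866) = 0.75

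**Upper limit from refusal alone.** If every woman with PCOS accepts and 75% accept overall, p′ = 0.134 / 0.75 = 17.9% (+4.5 points). Acceptance among the others is then (0.75 − 0.134) / 0.866 = 71.1%, so r = 1 / 0.711 = 1.41. If the 20% refusal is instead applied to all women regardless of the other losses, acceptance is 80% and the limit is 0.134 / 0.80 = 16.8% (+3.4 points).

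**Could BMI reveal it indirectly?** Take r = 1.25 with 75% acceptance.

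- Acceptance is 0.75 / 1.0335 = 72.6% without PCOS and 1.25 × 72.6% = 90.7% with it.
- PCOS prevalence is 16.2% among acceptors and 0.134 × (1 − 0.907) / 0.25 = 5.0% among refusers, a gap of 11.2 points.
- Assume that mean BMI differs by 0.2 to 0.5 SD between women with and without PCOS (not given in the documents). The BMI gap between acceptors and refusers is then 0.112 × 0.2 = 0.02 SD to 0.112 × 0.5 = 0.06 SD.
- Of 990 approached, 60% = 594 accept and 20% = 198 refuse. The standard error of the gap is √(1/594 + 1/198) = 0.082 SD.
- The gap is therefore 0.27 to 0.68 standard errors, and a two-sided 5% test has power of about 6% to 11%.

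This presumes that height and weight are known for every refuser. Study procedure does not say that they are measured before a woman declines.

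**The case against.** **The register is not useless.** Selection acting through age or BMI could be seen and weighted for, and zone can be recovered because sampling is by zone and numbered house. A reader might infer that the register can neither detect nor correct any selection. The documents do not support that; the gap is specific to symptoms and to ethnicity. The listed fields are also the only evidence of content, since the form is not shown.

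**The protocol's wording is hedged.** It says that the comparison will help, and does not claim to remove the bias. Nor does it say that similar age and BMI would be reported as absence of bias. Both points stand. Even so, the hedged sentence credits the listed fields with a protection they barely give against symptom-driven refusal.

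**Large biases need more loss than refusal provides.** A reader might take r = 1.5, which gives 0.201 / 1.067 = 18.8%. With 75% acceptance this would require 0.75 / 1.067 = 70.3% of women without PCOS and 1.5 × 70.3% = 105% of women with PCOS to accept, which is impossible. It becomes attainable only if drop-out is added (50/80 retained). Women who drop out have enrolled and may already have CRF data, which the withdrawal section keeps unless they ask for deletion. That loss can therefore be examined without the register.

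**The ratio and its sign are unknown.** The pair 0.8 and 1.25 stays within the planned 3 points. This is fair, and the figures show sensitivity only; they do not predict a bias.

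**Weighting has a limit.** The inclusion criteria admit only women with at least one of two features, so women with neither have no chance of taking part and no weight can be formed for them. This stands. It restricts what weighting can deliver but does not remove the case for recording the items.

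**Conclusion.** The concern holds in a limited form. As listed, the register supports a comparison on age, BMI and blood pressure only. That comparison cannot detect refusal driven by menstrual or androgenic symptoms, refusers are not contacted again, and no non-response analysis is planned. The sentence in Quality assurance promises more than these data can give.

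Under assumed ratios of 0.8 and 1.25 the estimate moves from 13.4% to 11.0% or 16.2%. Ratios of about 0.75 or 1.27 equal the full planned error. Refusal of 20 in 80 caps the upward bias at 4.5 points (17.9%). These figures take 13.4% as the true value in the population the plan intends to describe, and assume that refusal is the only loss related to PCOS status.

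The symptom-based inclusion criterion is a separate problem for the prevalence estimate, and nothing here resolves it.

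**What to change.** 1. At the household prescreen, record for every woman approached who allows it the yes/no answers to the two feature questions in the inclusion criteria. Add ethnicity, and the zone already known from sampling. Hold these under a study number, apart from name and phone number, with ethics approval for keeping them on refusers.
2. Prespecify in the statistical section a comparison of participants with refusers on these items.
3. Beside the unweighted prevalence, report one weighted for participation by feature pattern, age, BMI and zone, among women eligible to take part. State for how many refusers BMI is available.
4. State that weighting cannot represent women with neither feature while the inclusion criteria exclude them.
5. Reword the Quality assurance sentence so that the comparison is said to *help assess, and where possible adjust for, self-selection on the recorded items*.

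The cost is a few register columns and one further analysis, ethics approval and confidentiality handling for refuser data, and a slightly wider confidence interval for the weighted estimate. The prescreen must already establish the two features, so only ethnicity is a new question.
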